### Study Drug Treatment Compliance

Treatment compliance will be calculated as a percentage based on the total dose received (mg) divided by the adjusted planned administration (mg) (extent of exposure after adjusting for any dose modifications or holds).

Adjusted planned administration (mg) will be calculated based on the number of days of planned dose multiplied by 400 (mg). Number of days of planned dose will be defined as the cycle duration or days until end of treatment (whichever was smaller) for each planned dose per cycle minus the number of days dose held as reported on the Study Drug Administration CRF.

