| Dose Holds/
Modifications | 
Subjects will have their dose of SPH4336 adjusted in response to SPH4336-related toxicity as follows:
 

• Grade 1 or 2

○ No dose hold required

• Grade 3

○ Hold dosing until toxicity has resolved to at least Grade 1 or baseline

○ Reduce dose for second occurrence by at least 100 mg

○ Permanently discontinue further SPH4336 administration for third occurrence

• Grade 4 anemia or neutropenia

○ Restart dosing only if recovery to <math>\leq</math> Grade 1 occurs in <math>\leq</math> 14 days, otherwise permanently discontinue

○ If resumed, reduce dose by at least 100 mg

• Grade 4 lymphopenia

○ Hold dosing until toxicity has resolved to at least Grade 1 or baseline

○ If resumed, reduce dose by at least 100 mg

• All other Grade 4

○ Permanently discontinue further SPH4336 administration

 |
| Sample size                  | 
The following assumptions were used to determine sample size: Based on historical data, PFS at 12 weeks of <math>> 60\%</math> is considered promising and a PFS of <math>< 35\%</math> is considered not promising. A sample size of 29 subjects provides at least 90% power with type I error rate of 0.1 to decide whether the PFS rate at 12 weeks is less than or equal to 0.35 or greater than or equal to 0.60. If the number of subjects who are progression-free at 12 weeks is 14 or more, the hypothesis that the PFS rate at 12 weeks is less than or equal to 35% is rejected. If the number of subjects who are progression-free at 12 weeks is less than 14, the hypothesis that the PFS rate at 12 weeks is greater than or equal to 60% is rejected. Sample size was calculated using a single-stage Phase 2 clinical trial design. A final sample size of 33 will be utilized to account for a non-evaluable rate of 15%.
   |

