**Table 3: Dose Hold Secondary to SPH4336-related Toxicity**

| Toxicity (CTCAE Grading)       | Dose Hold   | Dose modification on resumption  |
|--------------------------------|---|--|
| 1 or 2                  | No dose hold required   | None   |
| 3                       | Hold dosing until toxicity has resolved to at least Grade 1 or baseline                                       | First occurrence (of same AE): No dose reduction
Second occurrence: Reduce dose by at least 100 mg
Third occurrence: Permanently discontinue |
| 4 anemia or neutropenia | Restart dosing only if recovery to $\leq$ Grade 1 occurs in $\leq$ 14 days, otherwise permanently discontinue | First occurrence (of same AE): Reduce by at least 100 mg
Second occurrence: Permanently discontinue   |
| 4 lymphopenia           | Hold dosing until toxicity has resolved to at least Grade 1 or baseline                                       | First occurrence (of same AE): Reduce by at least 100 mg
Second occurrence: Permanently discontinue   |
| 4 (non-hematologic)     | N/A, permanently discontinue  | N/A, permanently discontinue   |

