#### **6.6.3 Dose re-escalation**

In subjects who undergo dose reduction, re-escalation may be considered if the following criteria are met:

- The toxicity responsible for the prior dose reduction is considered unlikely with return to the prior higher dose based on a change in subject status or treatment (e.g., successful medical management of underlying condition, uncertain relationship of prior toxicity to SPH4336); and,

- Approval of the Medical Monitor.

After dose reescalation, if the toxicity recurs and requires another dose reduction, the subject is not allowed to return to the higher dose level.

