### Study Drug Exposure

Study drug exposure will be summarized by duration of exposure (days), total dose received (mg) and daily dose (mg) received.

Duration of exposure will be presented in days and is defined as the number of days from the date of First Dose to the date of Last Dose calculated as:

*(the date of last dose – date of first dose + 1)* and corrected for any days dose was held.

Total dose received (mg) will be calculated as the (sum of all tablets dispensed – sum of all tablets returned) x (100 mg) + (sum of all tablets dispensed – sum of all tablets returned) x (200 mg). If the number of tablets dispensed or returned is missing, it is assumed that the number of tablets returned was 0.

Daily dose received (mg) will be calculated as total dose received (mg) / duration of exposure in days for each subject.

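### The compliance denominator is described as adjusted for dose modifications, but its formula stays at 400 mg for every day not held

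*SAP*

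**What the plan says.** SAP 3.3.9, under Study Drug Treatment Compliance, defines compliance as total dose received (mg) over adjusted planned administration (mg), as a percentage. It gives the denominator twice.

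- In words, the denominator is the "extent of exposure after adjusting for any dose modifications or holds".
- As a calculation: "Adjusted planned administration (mg) will be calculated based on the number of days of planned dose multiplied by 400 (mg"). The day count is the shorter of the cycle length and the time to end of treatment, "minus the number of days dose held as reported on the Study Drug Administration CRF".

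The protocol starts every subject at 400 mg once daily but provides for other doses. For a Grade 3 related toxicity the synopsis has "Reduce dose for second occurrence by at least 100 mg", and Table 3 has "Second occurrence: Reduce dose by at least 100 mg". Table 3 also reduces the dose at the first Grade 4 anemia, neutropenia or lymphopenia if dosing resumes. Section 6.6.3 adds: "In subjects who undergo dose reduction, re-escalation may be considered if the following criteria are met". Section 9.3 lets the Safety Review Committee adjust the dose or schedule for the study.

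SAP 5.6 summarizes and lists compliance for the Safety Population (Table 14.1.6, Listing 16.2.5.3).

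**The concern.** The two statements cannot both be programmed for a dose-reduced subject. The description promises adjustment for holds and for modifications. The calculation removes held days and then values every remaining day at 400 mg, whatever was prescribed.

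A reduction made under the protocol would then look like missed tablets. The study closed for lack of efficacy, so a reader may well ask whether patients took the drug as directed, and the compliance column is where that reader will look.

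**Working it through.** The plan states no compliance figure, so there is none to reproduce. The check compares the two denominators for the same subject.

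**Inputs from the documents:** 400 mg daily starting dose (protocol synopsis); 28-day cycles (protocol section 4); reductions of at least 100 mg (synopsis, Table 3); the formulas in SAP 3.3.9.

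**Assumptions, for illustration only:** 84 days of treatment (three cycles), reduced doses of 300 mg or 200 mg, the timing shown, and every prescribed tablet taken.

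**Formulas**

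- As calculated in the SAP: total mg taken / [(days − held days) × 400].
- As described in the SAP: total mg taken / sum over non-held days of the mg prescribed that day.

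For a fully adherent subject the first reduces to mean prescribed dose on non-held days / 400. The second is always 100%.

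| Prescribed, all taken | mg taken | Calculated denominator (mg) | Calculated | Described |
|---|---|---|---|---|
| 300 mg, 84 days | 84 × 300 = 25,200 | 84 × 400 = 33,600 | 75.0% | 100% |
| 200 mg, 84 days | 84 × 200 = 16,800 | 33,600 | 50.0% | 100% |
| 400 mg for 28 days, then 300 mg for 56 | 11,200 + 16,800 = 28,000 | 33,600 | 83.3% | 100% |
| 400 mg for 28 days, 7-day hold, then 300 mg for 49 | 11,200 + 14,700 = 25,900 | 77 × 400 = 30,800 | 84.1% | 100% |

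The last row confirms that the hold is handled correctly and the shortfall comes only from the reduction.

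**The error can run the other way.** A subject prescribed 300 mg who takes 400 mg for 84 days scores 33,600 / 33,600 = 100% as calculated, against 33,600 / 25,200 = 133.3% as described.

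**Loss of information.** The SAP also reports daily dose: "Daily dose received (mg) will be calculated as total dose received (mg) / duration of exposure in days for each subject". That duration is corrected for held days too. Where the two day counts agree, calculated compliance is therefore just daily dose / 400. Two different subjects become indistinguishable:

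- prescribed 300 mg, all 84 doses taken: 25,200 mg, daily dose 300 mg, compliance 75%;
- prescribed 400 mg, 21 of 84 doses missed: 63 × 400 = 25,200 mg, daily dose 300 mg, compliance 75%.

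The described denominator separates them, at 100% and 75%.

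**Effect on the table.** SAP 5.7.2 reports fourteen patients enrolled. If all are in Table 14.1.6, one fully adherent subject at 300 mg throughout lowers mean compliance by 25 / 14 = 1.8 percentage points and could set the minimum at 75%.

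**The case against.** The best defence of the text is that the day count is defined separately for each planned dose within a cycle. This could mean that days are tallied by dose level, with 400 mg written as the default. That wording governs how days are counted; the multiplier remains a single 400. If tallying by dose level was intended, the formula still has to say so.

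The second objection is size, and it stands. No document reports that any subject was reduced. Under Table 3 a first Grade 3 event brings no reduction, so a reduction needs a recurrence or a specified Grade 4 hematologic event. Compliance is descriptive, the trial is small, and an abbreviated report is planned.

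The third objection is that reductions will be visible elsewhere, and it stands in part. Study drug administration and accountability are listed by subject (16.2.5.1, 16.2.5.2), and protocol 10.6 plans a summary of dose modifications and delays. But SAP 5.6 does not carry that summary over, and the SAP's table list has no separate table for it. Mean daily dose does not help, as shown above.

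A reader might also infer that the missing-count rule is a second error: "If the number of tablets dispensed or returned is missing, it is assumed that the number of tablets returned was 0". The documents do not support that. It is a stated convention and is exact when no tablets were left over. Total dose, daily dose and compliance may be biased upward only if untaken tablets lie behind a missing count, and the documents give no dispensing quantity from which to size this.

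**Conclusion.** The point holds as an internal contradiction in SAP 3.3.9. The stated calculation does not deliver the stated adjustment, and it understates compliance for a fully adherent dose-reduced subject. The percentages follow from the formulas; the reduced doses, the timing and the 84-day period behind them are assumptions.

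The importance is minor. The error appears only where a subject's prescribed dose differed from 400 mg, and the number of such subjects is unknown. For subjects kept at 400 mg the two denominators agree, with or without holds.

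A reader might infer that the contradiction casts doubt on the efficacy conclusion or on the decision to stop. It does not. The primary endpoint, duration of exposure and the futility evaluation make no use of the compliance percentage. Nor do the documents show that any reported compliance value is actually wrong. The point concerns how the SAP scores a prescribed dose and takes no position on which dose is right.

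**What to change.** Choose one of two changes, according to what the case report form holds.

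- **If prescribed dose by date is recorded:** define adjusted planned administration as the sum, over non-held days, of the dose prescribed on that day. It must be the prescribed dose and not the dose taken, or the ratio becomes circular.
- **If it is not recorded:** keep the calculation, delete dose modifications from the description, and label the result in Table 14.1.6 and Listing 16.2.5.3 as percent of 400 mg per non-held day.

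The first costs a sentence in the SAP and a small programming change. The second costs only wording and labels. The case report form is not among the documents, so check its content first. If the SAP is already final, record the change in the clinical study report, as protocol 10.1 and SAP section 7 provide.

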### Adverse Event

An AE is any untoward medical event that occurs to a subject following signing of the study Informed Consent Form (ICF), whether or not the event is considered SPH4336-related. AEs will be recorded as those that occur following signing the ICF through the sooner of 28 days after the last dose of SPH4336 or until the start of additional anticancer therapy.

Treatment-emergent Adverse Event

A TEAE will be an AE that occurred during the study after the first dose of study drug. Treatment-emergent AEs will be recorded from the first administration of SPH4336 up to the sooner of 28 days after the last dose of SPH4336 or until the start of additional anti-cancer therapy. Additionally, it is assumed that an Adverse Event which was reported to have started on Day 1 occurred after the initiation of study drug.

Serious Adverse Event (SAE)

An SAE is any AE that results in any of the following outcomes:

- Death
- A life-threatening experience
- An inpatient hospitalization or prolongation of an existing hospitalization
- A persistent or significant disability/incapacity
- A congenital anomaly/birth defect
- An event that is not listed above, but that requires intervention to prevent one of the outcomes listed above also is considered a SAE

The following will be excluded from the definition of an SAE:

- Elective hospitalizations that are not in response to an AE
- Hospitalizations that are of less than 24 hours duration
- Hospitalization related to disease progression

Concomitant Medications

Concomitant medications are those medications taken on or after the initiation of SPH4336 and will be determined programmatically based on medication start date. This definition includes medications started prior to the initiation of SPH4336, but continuing concomitantly with SPH4336.

Prior Medications

Prior medications are those medications taken and discontinued prior to the initiation of SPH4336 and will be determined programmatically based on medication start date and end date.

**3.4.           TIMING OF ANALYSES**

The final analysis of the study will occur when accrual has ceased and no patients remain on study treatment or if the study is stopped for safety reasons or lack of study drug efficacy.

**4.           ANALYSIS POPULATIONS**

The populations for analysis will include the Safety Analysis Population and Efficacy-Evaluable Population. A PK report describing the PK analysis will be included as an appendix in the clinical study report. An analysis of the biomarkers was not performed. Since the study ended prematurely because of futility, a limited analysis of efficacy will be performed.

#### **4.1. SAFETY ANALYSIS POPULATION**

The Safety Population will include all subjects who receive at least one dose of SPH4336.

#### **4.2. EFFICACY-EVALUABLE POPULATION**

The protocol defined the Efficacy-Evaluable Population is to include all subjects who received at least 1 dose of SPH4336 and met at least one of the following 2 criteria: have at least 2 post-baseline disease assessments (including at Week 12) and received study treatment for at least 12 weeks without disease progression; or experience disease progression while on study treatment.

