## **5.7. EFFICACY ANALYSIS**

### **5.7.1. Primary Efficacy Endpoint**

The primary efficacy endpoint was to be the number and percentage of Efficacy-Evaluable subjects who had Progression-Free Survival (PFS) at 12 weeks. PFS is defined as the time interval from the date of the first dose of the SPH4336 until the first date at which disease progression is documented as assessed by the Investigator or date of death due to any cause, whichever occurs first. Subjects who were alive and progression-free at the time of data analysis were to be censored at the time of their last tumor assessment. Progression was evaluated by the investigator according to RECIST v1.1.

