### **5.7.2. Primary Efficacy Analysis**

Limited efficacy analyses (tabulations) will be performed because this study ended prematurely due to futility (lack of efficacy). A by-patient listing of the objective responses evaluated by the investigators will be included in the report. The listing and table displaying duration of dosing will display the number of subjects who were dosed for 12 weeks or more without disease progression, and subjects who experienced disease progression at any time during the study, which were the criteria for inclusion in the Efficacy-Evaluable analysis dataset.

After 13 patients were enrolled in the study, too few Efficacy-Evaluable patients had reached 12 weeks of dosing without disease progression (2 of 10) to obtain a positive result for the primary study objective (see Section 3.1 Sample Size and Power). A futility analysis was performed, and it showed that the study would most likely not reach the threshold for a positive signal, even if additional patients were enrolled. A fourteenth patient was enrolled, but the study was closed (due to futility) before week 12.

Bayesian Evaluation of Futility

# Efficacy-Evaluable Patients	Stop Study if #Responses ≤
10	2
11	3
12	3
13	4
14	4
15	5
16	5
17	6
18	6
29	13

The analysis above was performed using available software (BOP2: Bayesian Optimal Phase II Design with Simple and Complex Endpoints (mdanderson.org)) and a simulation was conducted evaluating different sample sizes between current enrollment at the time of the evaluation (n=8) and full protocol enrollment (n=29).

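### SAP 4.2 and SAP 5.7.2 define the Efficacy-Evaluable Population differently, and neither definition matches the PFS events in SAP 5.7.1

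*SAP*

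**What the plan says.** SAP 4.2 opens with "The protocol defined the Efficacy-Evaluable Population is to include all subjects" who received at least one dose and met one of two criteria. The first is two or more post-baseline assessments, one of them at Week 12, in a subject who "received study treatment for at least 12 weeks without disease progression; or experience disease progression while on study treatment"; the words after the semicolon are the second criterion.

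SAP 5.7.2 describes the same dataset again. It says that "The listing and table displaying duration of dosing will display the number of subjects" dosed for 12 weeks or more without progression, and "subjects who experienced disease progression at any time during the study, which were the criteria for inclusion in the Efficacy-Evaluable analysis dataset". It sets no minimum number of assessments and no on-treatment limit.

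Protocol 10.4.3 asks for at least one dose and either two post-baseline disease assessments or clinical progression. SAP Section 7 records the dropped efficacy and biomarker analyses and anticipates no other change.

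SAP 5.7.1 takes Efficacy-Evaluable subjects as the denominator for 12-week PFS. An event is documented progression or "date of death due to any cause, whichever occurs first", with no on-treatment restriction. The reported result is that "too few Efficacy-Evaluable patients had reached 12 weeks of dosing without disease progression (2 of 10" with 13 enrolled.

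**The concern.** A programmer cannot follow both 4.2 and 5.7.2. A subject who stops drug at week 5 and progresses at week 10 is out under one and in under the other. The protocol's rule that the SAP prevails (Protocol 10.1) settles protocol against SAP, not SAP against SAP.

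The population also does not fit its endpoint. Some subjects with a 5.7.1 event by Week 12 never enter the denominator, and neither do some subjects who are progression-free at Week 12 but stopped drug early. These cases are foreseeable: the plan allows stopping for toxicity or withdrawal of consent.

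What is at stake is descriptive. SAP 5 removes hypothesis testing and SAP 9 lists no 12-week PFS table. What remains is the 2 of 10 cited as the basis for closure, and Table 14.2.1 (Best Overall Response), whose population is Efficacy. That table leaves out treated subjects who are not evaluable, or who have stable disease and stop before Week 12 without progression, although SAP 3.3.7 provides a not-evaluable category.

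**Working it through.** **1. Criteria side by side**

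| Element | Protocol 10.4.3 | SAP 4.2 | SAP 5.7.2 |
|---|---|---|---|
| Assessments, if no progression | at least 2 post-baseline | at least 2, including Week 12 | none stated |
| Time on drug, if no progression | at least 1 dose | at least 12 weeks | at least 12 weeks |
| Progression | clinical, no on-treatment limit | only while on drug | any time in study |
| Death without documented progression | not mentioned | not mentioned | not mentioned |

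**2. Test cases**

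| Case | Status under 5.7.1 | SAP 4.2 | SAP 5.7.2 |
|---|---|---|---|
| A. Stops at week 5, progresses off drug at week 10 | event | out | in |
| B. Dies at week 6, no documented progression | event | out | out |
| C. Dosed 12 weeks or more without progression, but one assessment only or no Week-12 scan | no event recorded | out | in |
| D. Stops at week 5, progression-free at a Week-12 scan, no later progression | no event by Week 12 | out | out |

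Case B generally fails Protocol 10.4.3 too: with scans every 6 weeks there is at most one scheduled post-baseline assessment by week 6, and no clinical progression. Adopting the 5.7.2 wording alone would therefore rescue A but not B. Losing A or B pushes the 12-week rate up; losing D pushes it down.

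**3. The plan's own rule**

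Inputs (SAP 3.1): n = 29, success at 14 or more, rates 0.35 and 0.60. Exact binomial:
- P(X ≥ 14 | 29, 0.35) = 0.098, within the stated 0.1.
- P(X ≥ 14 | 29, 0.60) = 0.929, above the stated 90%.

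The design figures reproduce. The conflict lies in who is counted.

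**4. Effect on the reported rate**

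Reported: 2/10 = 20.0%, exact (Clopper-Pearson) 95% CI 2.5% to 55.6%.

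Uncounted at that point: 13 − 10 = 3. The SAP does not say whether they were excluded or had not yet reached Week 12. Assume k of them were excluded, k = 0 to 3. Adding them back gives a range from 2/(10+k), all failures, to (2+k)/(10+k), all progression-free. The last two columns compare the maximum count with the stop lines in SAP 5.7.2.

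| k | Lowest (95% CI) | Highest (95% CI) | Stop if count ≤ | Highest count clears the line? |
|---|---|---|---|---|
| 0 | 2/10 = 20.0% (2.5–55.6) | 2/10 = 20.0% (2.5–55.6) | 2 | no |
| 1 | 2/11 = 18.2% (2.3–51.8) | 3/11 = 27.3% (6.0–61.0) | 3 | no |
| 2 | 2/12 = 16.7% (2.1–48.4) | 4/12 = 33.3% (9.9–65.1) | 3 | yes (4 > 3) |
| 3 | 2/13 = 15.4% (1.9–45.4) | 5/13 = 38.5% (13.9–68.4) | 4 | yes (5 > 4) |

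Only 4/12 and 5/13 clear a line. Each needs every excluded subject to be progression-free at Week 12, and at least two of them. With k = 3 and two progression-free, 4/13 still meets the stop line of 4.

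**The case against.** Several points on the other side stand.

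- **Early deaths are not specific to SAP 4.2.** They also fail 5.7.2 and generally Protocol 10.4.3, and Protocol 4.8 builds non-evaluability and replacement into the design. That part is inherited.
- **Little planned output depends on this.** SAP 5.7.2 and 5.7.3 cut efficacy to tabulations. The 12-week counts appear to belong to Safety Population outputs (14.1.6, 16.2.5.3), and response, deaths and disposition are already listed for that population. With at most 14 subjects, a reader could rebuild much of this. The listings still would not say who was excluded, why, or which wording produced 2 of 10.
- **Off-drug Week-12 status may not exist.** Table 1 marks no tumor assessment after the end-of-treatment visit, and long-term follow-up is 3-monthly, possibly by record review. A remedy cannot assume every such status is known.

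A reader might infer that the criteria were rewritten after the futility look. The documents do not date the change. The past tense in 5.7.2 fits equally well with criteria already in use at the look, and an amendment later than version 1.0 cannot be ruled out.

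A reader might also compare 10 evaluable with 14 enrolled to size the effect on Best Overall Response. That mixes time points: the 10 were counted with 13 enrolled, while Table 14.2.1 is made at the final analysis, when subjects pending at the look may have become evaluable.

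**Conclusion.** The inconsistency is real on the text: two definitions of one dataset, neither aligned with 5.7.1, and an attribution that the supplied protocol does not support. It should be fixed, but its effect is limited to descriptive reporting of the 12-week rate and Best Overall Response. Under the assumption that 0 to 3 of the uncounted subjects were excluded, the rate could range from 15.4% to 38.5% against the reported 20.0%.

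It would be tempting to conclude that the exclusions undermine the futility decision. The documents do not support that. Restored failures only lower 2/10, and clearing a stop line needs at least two excluded subjects, all progression-free at Week 12; no such subject is documented. Nor is the bias known to run one way, since early stoppers who remain progression-free are dropped as well. The documents give no count for any of these groups.

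**What to change.** 1. Use one definition in SAP 4.2 and 5.7.2. Documented progression, on or off drug, or death from any cause by Week 12 is an evaluable failure. Progression-free at an available Week-12 assessment is a success, whether or not the subject is still on drug.
2. This set still depends partly on outcome, so report beside it the 12-week progression-free count in all treated subjects with exact 95% CI. Give separate rows to subjects whose Week-12 status is unknown, including early stoppers with no off-drug assessment, and to subjects who had not reached Week 12 at closure. The SAP names one candidate for the latter: "A fourteenth patient was enrolled, but the study was closed (due to futility) before week 12".
3. Tabulate Best Overall Response in the Safety Population with a not-evaluable row.
4. List each exclusion with its reason, and state which wording gave 2 of 10. Reconcile that with the 13 enrolled and the n=8 that 5.7.2 gives as enrollment at the evaluation.
5. Correct the attribution to the protocol, or cite the amendment that made the change. Record the change in Section 7 with its actual date, without presuming that it followed the futility look.

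The cost is SAP wording, one summary line, a few table rows and a reason per excluded subject, with no protocol amendment. Most of the data are already planned for listing. The downside is two denominators to explain, a rate that may move either way, and some off-drug Week-12 statuses that may stay unknown.
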